## I. Background and significance

### A. *Treatment of MDD:*

Over two-thirds of patients with MDD treated with first-line medications, such as citalopram, fail to achieve remission during 12 weeks of acute treatment. Patients who fail to achieve remission typically have greater impairment of social and work function and a much higher risk of relapse and recurrence of MDD than those who remit (Paykel et al., 2005). As demonstrated in the STAR\*D trial, many patients who go on to achieve remission on pharmacotherapy or CBT do not do so until the second 6 weeks of treatment even with enhanced, measurement-based care (Rush et al., 2006).

Recently, an increasing body of “predictor studies” has emerged which aims to use neuroimaging measures to predict treatment outcomes. These studies are pivotal in advancing treatment options for depression, as validated surrogate markers that predict response at baseline or soon after starting treatment would help clinicians optimize a patient’s treatment within the first several weeks of initiation, potentially saving weeks to months of ongoing distress, disability and risk of suicide. In light of the challenges that MDD poses to clinicians and patients alike, identifying biomarkers which are able to predict outcome are urgently needed to help further refine the standard of care for depression. Additionally, to our awareness no studies have used neuroimaging measures to directly compare different psychosocial interventions, such as Cognitive Behavioral Therapy (CBT).

### B. *Functional Brain Changes Related to Response to CBT:*

Functional brain imaging has suggested the possibility that pharmacotherapy and psychotherapy, while both representing effective treatments for MDD, may exert their effects through different mechanisms (Goldapple et al., 2004). CBT is seen as having a “top down” effect, while pharmacotherapy is viewed as generating a “bottom up” neurobiological cascade. Despite the strong evidence base and widespread use of CBT for depression, we still know very little about its biological mechanisms of action, and even less about biological predictors of response to CBT. The identification of early predictors of response using QEEG might further our understanding of the mechanisms underlying the efficacy of CBT in MDD.

### C. *QEEG:*

Quantitative electroencephalography (QEEG) has emerged in recent years as a technology that may help predict eventual response to antidepressants as early as the first week of prescription and may help shed light on the mechanism(s) of action of depression treatments. QEEG has enabled spectral analysis of EEG signals using a digitized signal on magnetic or optical media, providing information that cannot be extracted through visual inspection of the traditional EEG paper tracings. Cordance, a QEEG measure integrating absolute and relative power of the signal, was shown to be decreased in subjects with MDD, compared to normal

subjects (Cook et al, 1998). Researchers have reported differences between responders and non-responders to antidepressant treatment with respect to the absolute or relative power of the EEG signal (Ulrich et al., 1994; Knott et al, 1996). Subsequently, QEEG has been shown to have utility in predicting clinical response to SSRI antidepressants (Cook et al, 1999). Specifically, in a case series, Cook and Leuchter (2001) found that clinical response to antidepressant medications was preceded by decreases in QEEG measurements (theta cordance) in the prefrontal brain regions.

#### *D. Reward Responsiveness Task*

This study will also utilize the Signal Detection computer task which measures anhedonia, the loss of pleasure or lack of reactivity to pleasurable stimuli (APA 1994), and has been considered a trait marker related to vulnerability for depression (Loas 1996; Meehl 1975). Depression has been found to be associated with low levels of self-reinforcement (Gotlib 1982); diminished emotional response to pleasant cues (Berenbaum and Oltmanns 1992; Sloan et al 2001); underestimation of the frequency of positive reinforcements received (Buchwald 1977); decreased responsiveness to reward (Hughes et al 1985); and decreased spatial attention to positive but not negative facial expression (Suslow et al 2001). Previous behavioral studies indicate that depressed individuals and subjects with elevated depressive symptoms show altered reward processing as compared with controls, but normal punishment processing (Henriques & Davidson, 2000). The Signal Detection Task has been implemented in a non-depressed sample as well as schizophrenic samples and has shown that increased levels of depressive symptoms are associated with decreased responsiveness to reward cues.

#### *E. Summary and Rationale:*

Studies which identify validated surrogate markers at baseline or soon after starting treatment that can predict response to treatment have the potential to refine the standard of care for depression, as these predictor studies will reduce the amount of time that clinicians spend adjusting treatments to find the most optimal treatment option. Additionally, studies which compare predictive biomarkers between treatments, particularly between psychotherapy and pharmacotherapy, will further enable clinicians to choose an optimal treatment.

To our knowledge, QEEG has not been studied in the prediction of response to CBT, an important and widely used non-pharmacologic approach to treating depression. Establishing QEEG technology as a predictor of response to CBT could help to guide treatment selection for individual patients. It is probable that certain patient populations are more likely to respond to either psychotherapeutic or psychopharmacological interventions, while others may benefit from a combination of treatment modalities. The public health significance of a valid technology that provides an objective means of determining likelihood of response to treatment would be enormous. This study will provide preliminary information about the utility of QEEG as a predictor of response in psychotherapy and will furnish the knowledge base of QEEG changes related to clinical variables, providing pilot data for a study in a larger sample.

Additionally, very few studies have assessed changes in reward responsiveness as a function of treatment. It is possible that CBT and pharmacological interventions have different effects on reward responsiveness and anhedonia, and thus the use of this task will allow us to investigate the influence of different treatments on reward processing in this population. We expect that the results of this study will guide future research with the ultimate goal of identifying a behavioral indicator of underlying dysfunction in reward related brain regions. Finally, it is possible that the reward responsiveness will act as a predictor of response to both psychotherapy and pharmacological treatment.

## **II. Specific Aims:**

Primary Aim 1: To determine whether QEEG technology can predict whether a patient with MDD will respond to CBT.

Hypothesis 1: Clinical response (defined as >50% change in HAMD-17 from beginning to endpoint) will correlate with changes in QEEG metrics (ATR, EEG Bispectrum, cordance estimates) from beginning to two weeks after starting treatment.

Primary Aim 2: To determine whether there are unique biological changes in patients undergoing CBT, as measured by the QEEG, that are different than those associated with antidepressants (SSRIs).

Hypothesis 2: QEEG parameters, different from those that predict response to pharmacotherapy, will be associated with response to CBT.

Secondary Aim 1: To determine whether there are correlations between QEEG patterns and changes in clinical functioning, assessed by clinical and self-rated instruments (SF-36, Symptom Questionnaire, Beck Depression Inventory), in both arms (CBT vs. escitalopram).

Secondary Aim 2: To determine whether there are any correlations between QEEG metrics and clinical variables (gender, age, comorbid anxiety, chronicity of depression).

Secondary Aim 3: To determine whether the behavioral processes associated with reward responsiveness in a depressed population change as a function of treatment.

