## VI. Statistical Analysis

- a) *Statistical Plan:* The Mann-Whitney U test will be used to analyze differences in changes of QEEG between responders and non-responders to CBT. We will use logistic regression with the outcome being response/no response on the HAMD-17 and the predictors being other EEG measures. We will test the predictors in a stepwise manner given the limited power with a small N. A power calculation based on a previous QEEG study conducted in our clinic reveals that, to achieve power = 0.80, we would need 34 subjects per group. With N = 30 per group (60 subjects total), our power is 0.76. Power for the current study, with N = 15 per group, is 0.47. While this study is underpowered due to the small N, the goal of this study is to act as a pilot study which can help measure effect sizes, providing a foundation for future, larger projects.

For secondary aims, we will use Pearson r's for pairs of continuous measures, or point-biserial r for pairs of dichotomous and continuous measures.

Data from the Signal Detection Fact Task will be analyzed by [name] at Harvard University. Response bias will be the main variable of interest, whereas reaction time, hit rates, and discriminability values will provide control variables. Analyses of variance (ANOVAs) will be used to investigate variables across the three blocks. Discriminability and response biases will be computed using standard formulae (e.g. McCarthy and Davidson 1981).

- b) *Study Endpoints:* Endpoints will be defined as the final study visit at the end of the 12 weeks, or the termination/final visit for patients who choose to (or have to) end participation in the study prematurely.

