### **VIII. Potential Benefits**

- a) *Potential benefit to individuals*: The study will potentially provide relief of depressive symptoms to participating patients. Subjects will also be compensated \$25 per QEEG (\$125 total for all 5 QEEGs), and will receive \$20 plus earnings per trial of signal detection (\$40 plus earnings in total). Subjects will also be offered up to \$25 travel reimbursement per visit.
- b) *Potential benefit to society*: This proposal investigates QEEG in the prediction of response to both CBT and escitalopram in patients with major depressive disorder. Establishing QEEG technology as a predictor of response to therapy and/or medications could help guide treatment selection for individual patients. Thus, the study will potentially further our understanding of the neurobiological differences which underly individual differences in responses to certain treatments. The study would be one of the first comparisons of baseline biomarkers between patients who respond to CBT versus those who respond to an SSRI, thus filling an important gap in our knowledge base of predictors of response to different treatments. Establishing QEEG as an accurate predictive tool would have an enormous impact on providing better care to patients suffering from major depressive disorder.

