Quantitative Electroencephalogram (QEEG) Predictors of Response to Psychotherapy
Versus Antidepressant Treatment in Depression

Identifiers: NCT00824044

Unique Protocol ID: 2008-P-000838

Date prepared: 12/7/2017

Summary:

A-priori expectation from prior **medication** work is a decrease in theta activity from baseline at week 1 in responders, and an increase in non-responders. Prior work showed an increase in theta activity in **placebo** responders (and little change in non-responders). (See attached manuscript that describes changes in theta Cordance over time in both placebo and medication groups. See Fig 4 on page 128.) Also, ATR is expected to be higher in medication responders than non-responders after 1 week on antidepressant.

Methods:

ATR and Power metrics were calculated from available EEGs at baseline and subsequent visits. Change in Power between baseline and subsequent visits were derived. The data were analyzed for 3 groups: Pooled, Drug-only, Drug+CBT.

In a completer analysis (not an intent to treat), independent sample t tests were used to assess the relationship between responders (greater than or equal to 50 % reduction in the primary outcome (HAMD-17 score)) and change in QEEG metrics across time.

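### Primary Aim 1 is about predicting a patient's response to CBT, but neither document plans a measure of predictive accuracy or any validation, so a positive result would show association only

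*Protocol*

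**What the plan says.** Protocol section II sets Primary Aim 1: "To determine whether QEEG technology can predict whether a patient with MDD will respond to CBT". Hypothesis 1, directly beneath it, is worded as an association: clinical response "will correlate with changes in QEEG metrics (ATR, EEG Bispectrum, cordance estimates) from beginning to two weeks after starting treatment".

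Protocol section VI a) plans two analyses that bear on this aim:

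- A group comparison: "The Mann-Whitney U test will be used to analyze differences in changes of QEEG between responders and non-responders to CBT".
- A model of response: "We will use logistic regression with the outcome being response/no response on the HAMD-17 and the predictors being other EEG measures". Predictors enter stepwise: "We will test the predictors in a stepwise manner given the limited power with a small N".

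The SAP Methods describe a completer analysis in which "independent sample t tests were used to assess the relationship between responders" and QEEG change. On populations they say: "The data were analyzed for 3 groups: Pooled, Drug-only, Drug+CBT". Neither the Mann-Whitney test nor the logistic regression appears there, and no group is named as CBT alone.

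Neither document mentions an AUC, sensitivity, specificity, predictive values, a cut-off, calibration or a validation step.

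Section VI a) calls the study an underpowered pilot meant to measure effect sizes. Section VIII b) gives the longer-term ambition: "Establishing QEEG as an accurate predictive tool would have an enormous impact".

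**The concern.** A test of difference asks whether QEEG change is distributed differently in responders and non-responders. A prediction aim asks how often QEEG would sort a patient correctly. A moderate, real difference can coexist with substantial misclassification, so the first answer does not supply the second.

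Two misreadings are at stake. A small p value could be reported as showing that QEEG predicts response to CBT, with no estimate of how well. A large p value could be reported as showing that it does not, although a sample this small could not exclude a useful marker.

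There is also a risk in the opposite direction. If accuracy is worked out later, in the same few patients used to choose the metric and the cut-off, it will look good even when the marker is noise. Stepwise selection adds to that optimism, and no correction is planned.

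**Working it through.** **Inputs from the documents.** Protocol section VI a): power 0.80 with 34 per group, 0.76 with 30, 0.47 with 15. Sections IV and V: 30 patients randomized 1:1, so 15 to CBT. Hypothesis 1: three metrics (ATR, bispectrum, cordance).

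**Assumptions.** The documents do not give alpha, sidedness, effect size or the CBT response rate. I take two-sided 5%, a normal marker with equal variances, and a 7/8 split of the 15 CBT patients. I also assume that the effect behind the power statement applies to responders against non-responders; the protocol does not say which groups or metric it came from.

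**1. Reproduce the stated power.** With the normal formula, d = (1.960 + 0.842) × √(2/34) = 0.679. Power = Φ(d√(n/2) − 1.960) then gives 0.749 at n = 30 (stated 0.76) and 0.461 at n = 15 (stated 0.47). The two-sided t test gives d = 0.690, with powers 0.747 and 0.446. The figures are thus close to a two-group comparison of means. The 34 per group was used to derive d, so only the other two figures are checks.

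**2. Turn that effect into accuracy** (d = 0.690).

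- AUC = Φ(d/√2) = Φ(0.488) = 0.687.
- Sensitivity = specificity at the midpoint cut = Φ(d/2) = Φ(0.345) = 0.635, so about 37% of patients would be misclassified.

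**3. Precision in the CBT arm** (Hanley-McNeil). With A = 0.687, Q₁ = A/(2 − A) = 0.523 and Q₂ = 2A²/(1 + A) = 0.560:

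SE² = [A(1 − A) + (n₁ − 1)(Q₁ − A²) + (n₂ − 1)(Q₂ − A²)]/(n₁n₂) = [0.2150 + 6 × 0.0512 + 7 × 0.0876]/56 = 0.0203, so SE = 0.142.

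| Responders / non-responders | SE | 95% CI for AUC |
|---|---|---|
| 7 / 8 | 0.142 | 0.41 to 0.97 |
| 5 / 10 | 0.155 | 0.38 to 0.99 |
| 10 / 5 | 0.143 | 0.41 to 0.97 |

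If the protocol's 15 per group means the treatment arms, t-test power for a 7 v 8 contrast at this effect is about 0.24.

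**4. Optimism of unvalidated accuracy.** I simulated pure-noise metrics in 7 v 8 patients and took the best cut, in either direction, in the same patients. Mean accuracy is about 70% for one metric and about 75% for the best of three independent metrics. With the direction fixed in advance, one metric averages 64%. All of these match or exceed the 63% that a real effect of d = 0.69 would deliver.

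**5. What the planned rank test already contains.** AUC = U/(n₁n₂). At 7/8 the exact two-sided Mann-Whitney test reaches p < 0.05 when the smaller U is 10 or less (p = 0.040; U = 11 gives 0.054), that is, at an observed AUC of at least 1 − 10/56 = 0.82. The AUC is one division away from the planned statistic, but nothing in either document says it will be reported.

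**The case against.** The best defence has four parts.

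*The protocol does more than compare averages.* This is correct. A reader of the SAP alone might infer that every planned analysis compares group means. The protocol does not support that: its logistic regression models each patient's probability of response, and Mann-Whitney works on ranks. What remains is that the regression has no stated accuracy output or validation, its population is not given, its predictors are described only as other EEG measures, and it does not appear in the SAP.

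*Hypothesis 1 is a correlation and the study is a declared pilot.* This is also correct, and it defeats the reading that the planned tests are useless for the aim. They give preliminary evidence on it. The sentence about an accurate tool describes a possible future benefit, not a result promised here. But the pilot's stated purpose is to measure effect sizes, and for a prediction aim the natural one is an AUC with its interval.

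*A significant result would not mean near-chance classification.* At 7/8, significance on the rank test requires an observed AUC of at least 0.82. The problem after a small p value is therefore optimism and imprecision; the documents do not support saying that classification in that sample would be close to chance.

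*The figures rest on assumptions.* They do, as listed in the working. They illustrate scale. The absence of an accuracy measure does not depend on them.

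**Conclusion.** The point holds in this form: Aim 1 is framed as prediction, no measure of predictive accuracy or validation is planned in either document, and the SAP narrows the analysis to t tests with no CBT-only set. Carried out as written, the plan can show association between QEEG change and response. It would not estimate how well QEEG classifies patients treated with CBT.

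On the stated assumptions, the effect implied by the protocol's own power statement corresponds to an AUC of about 0.69 and about 63% sensitivity and specificity. The interval for that AUC in 15 CBT patients runs from below 0.5 to near 1. Unvalidated best-cut accuracy from noise alone would average 70% to 75%.

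A reader might also infer that a lower AUC limit above 0.5 would establish prediction. It would not. That limit addresses essentially the same null hypothesis as the Mann-Whitney test; it shows discrimination better than chance and sets no standard of usefulness for individual patients.

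This should be corrected, but it does not invalidate the study as a pilot.

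**What to change.** In protocol section VI a) and the SAP Methods:

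1. Define a CBT-only analysis set for Aim 1.
2. Make the Aim 1 result the AUC, U/(n₁n₂), of each QEEG metric named in Hypothesis 1 at week 2, with an exact or bootstrap 95% CI.
3. Evaluate ATR on its existing 0 to 100 scale (protocol section V a), without refitting.
4. Give any sensitivity, specificity or logistic-model accuracy only as leave-one-out or bootstrap-corrected values, with the choice of predictors and cut-off repeated inside each fold or resample.
5. Describe the finding as a preliminary association, with its AUC and CI. State that a lower limit above 0.5 is not by itself evidence of useful individual prediction.

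The SAP is written in the past tense. If the data have already been analysed, label these results post hoc.

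The cost is some SAP wording and a little extra analysis, with no new data. The interval will be wide and will look less favourable than a bare p value. Leave-one-out figures from about 15 patients will also be imprecise and should be presented as such.

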#### **IV. Subject Enrollment**

*A. Methods of enrollment/registration/randomization:*

Patients are usually screened by telephone to determine tentative eligibility for studies. The subjects then are invited to come to MGH for a full psychiatric diagnostic interview. Patients accepted into the study will be registered through the Depression Clinical and Research Program. Randomization numbers will be provided by the study Biostatistician and will be maintained by the research pharmacists at MGH Research Pharmacy, who will administer the open label escitalopram, 10-20 mg/day, to those subjects who have been randomized to receive medication. The randomization will be 1:1, i.e. half of the patients will be randomized to receive escitalopram (10-20 mg/day, flexible dose) and half will be randomized to receive twelve weekly 50-minute

Cognitive Behavioral Therapy sessions. Both treatment interventions have been strongly validated by the literature, and are considered standard of care for this population.

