## V. Study Procedures

### a) *Study visits and parameters to be measured:*

The study involves the enrollment of 30 outpatients with major depressive disorder.

Patients screened for the study and found to be eligible will return for their baseline visit after one week, at which eligible patients (n = 30) will be randomized to either CBT or to standard pharmacotherapy with an SSRI (escitalopram 10-20mg) for 12 weeks.

The CBT group will receive twelve weekly 50-minute individual sessions over the course of 12 weeks conducted by experienced therapists who are trained in manual based CBT. The medication group will receive open label treatment of escitalopram, 10-20 mg/day, flexible dose, for 12 weeks, and will be seen every two weeks by a study physician. In both arms, study assessors, who are blind to treatment condition, will assess patients monthly (week 0, 4, 8, and 12), and are responsible for the primary outcome measure (HAMD-17).

The QEEG will be administered 5 times during the study (week 0, 1, 2, 8 and endpoint) allowing us to assess whether there are any correlations between QEEG patterns and changes in clinical functioning. We will record EEG from a fronto-parieto-temporal derivation using a 4-channel EEG Monitor (Aspect Medical Systems) connected to the subject via disposable EEG electrodes. The adhesive material of the electrodes is similar to that found in ECG electrodes. All recordings will be analyzed off-line to generate QEEG metrics. Once such QEEG metric, the ATR, is a complex index derived from left-right asymmetry of combined theta+alpha (4-12Hz) power, relative theta power, and percent change from baseline in relative theta power, and ranges from 0 (low probability of response) to 100 (high probability of response). De-identified data will be shared with Aspect Medical Systems for offline calculation of EEG-based metrics.

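### Every analysis planned for Hypothesis 1 reduces HAMD-17 to response at a 50% cut; for a pilot meant to measure effect sizes, an estimate using the continuous change should be added

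*Protocol*

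**What the plan says.** Protocol, II. Specific Aims, Hypothesis 1: "Clinical response (defined as >50% change in HAMD-17 from beginning to endpoint) will correlate with changes in QEEG metrics". The QEEG change runs from the start of treatment to two weeks, and three kinds of metric are named: ATR, bispectrum and cordance estimates.

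Protocol, VI. Statistical Analysis, gives two analyses for this hypothesis, both on the binary outcome: "The Mann-Whitney U test will be used to analyze differences in changes of QEEG between responders and non-responders to CBT", and "We will use logistic regression with the outcome being response/no response on the HAMD-17". The SAP's Methods also split by responder status: "independent sample t tests were used to assess the relationship between responders (greater than or equal to 50 % reduction in the primary outcome".

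Pearson and point-biserial correlations are reserved for the secondary aims. Secondary Aim 1 relates QEEG patterns to change in functioning on the SF-36, Symptom Questionnaire and BDI; HAMD-17 is not in that list. Blinded assessors score HAMD-17 at weeks 0, 4, 8 and 12 (V. Study Procedures).

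On size and purpose: "The study involves the enrollment of 30 outpatients with major depressive disorder"; "The randomization will be 1:1, i.e. half of the patients will be randomized to receive escitalopram". The protocol accepts that power is low and says "the goal of this study is to act as a pilot study which can help measure effect sizes".

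**The concern.** The study's product is an effect size on which to plan a larger trial. The primary measure is collected as a score but enters the Hypothesis 1 analyses only as one side or the other of a fixed threshold. A patient who improves by 48% is grouped with one who does not improve at all, and is separated from one who improves by 52%.

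Two things are at stake. The estimate is less precise than the collected data allow, and it depends on where the cut falls. The documents show this dependence themselves: Hypothesis 1 asks for more than 50%, the SAP for 50% or more. HAMD-17 takes whole numbers, so a patient going from 20 to 10 is a non-responder under one rule and a responder under the other. In a 15-patient arm, one such patient is 1/15, or about 7%.

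**Working it through.** **Inputs from the documents.** 30 patients randomised 1:1, so 30/2 = 15 in the CBT arm. The SAP analyses completers and no dropout rate is given, so 15 is an upper bound. Stated power (VI. Statistical Analysis): 34 per group for 0.80; 0.76 at 30 per group; 0.47 at 15 per group.

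**Inputs assumed.** Effect size, alpha and sidedness are not stated: I take two-sided 0.05 and solve for the effect size. The CBT response rate is not stated: I take 20% to 70%. QEEG change and HAMD-17 change are taken as bivariate normal.

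**1. The plan's own figures.** Power = Φ(d√(n/2) − 1.96). With d = 0.688:
- n = 34: Φ(2.837 − 1.96) = 0.81, and 34 is the smallest n reaching 0.80 (n = 33 gives 0.798)
- n = 30: Φ(2.665 − 1.96) = 0.76
- n = 15: Φ(1.884 − 1.96) = 0.47

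One d reproduces all three. This shows only that the figures agree with each other, because d was back-solved. The 0.47 is for 15 against 15. A responder comparison inside the CBT arm splits 15 patients: at 7 against 8 the same d gives about 0.26 (normal approximation) or 0.23 (t test).

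**2. Information kept after the cut.** For a normal outcome cut so that a proportion p respond, the fraction kept is φ(z_p)²/[p(1 − p)].

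| Response rate | Kept | Lost | 15 patients are worth |
|---|---|---|---|
| 50% | 0.3989²/0.25 = 0.637 | 36% | 9.5 |
| 40% or 60% | 0.622 | 38% | 9.3 |
| 30% or 70% | 0.576 | 42% | 8.6 |
| 25% | 0.539 | 46% | 8.1 |
| 20% | 0.490 | 51% | 7.3 |

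The 36% is the smallest possible loss under this model, not a typical one.

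**3. Translating d to a correlation.** With equal halves the point-biserial r is d/√(d² + 4) = 0.688/√(0.473 + 4) = 0.325. The cut attenuates by √0.637 = 0.798, so the latent correlation is 0.325/0.798 = 0.41.

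**4. Power at n = 15, latent correlation 0.41, 50% response rate (simulated).**
- Rank-based: Spearman on continuous change about 0.31; exact Mann-Whitney by responder status about 0.19
- Parametric: Pearson about 0.35; t test by responder status about 0.22

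**5. Sensitivity to the model.** Suppose instead that QEEG change differs only between two distinct response classes (d = 0.688, 7 against 8), with HAMD-17 change separated by 2 or 3 SD and patients classed by the observed cut. Spearman against the responder comparison is then about 0.15 v 0.14 at 2 SD and 0.18 v 0.19 at 3 SD: no material difference.

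**The case against.** The strongest reply is that the binary outcome is the question. Primary Aim 1 asks whether a patient will respond, Hypothesis 1 defines response as a threshold, ATR is described as a scale of response probability, and the SAP's prior expectation is framed by responder group. The verb in Hypothesis 1 does not imply a continuous outcome either, since the protocol itself uses point-biserial correlation for mixed pairs. All of this stands. A reader might infer that dichotomising makes the primary analysis wrong; the documents do not support that, and the responder analyses should remain.

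A reader might also call this a median split. It is not: the cut is a fixed 50% reduction, and the two coincide only if half the patients respond.

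Secondary Aim 1 already gives continuous symptom change through the BDI. That is a partial remedy, but not for the primary measure or for Hypothesis 1.

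Precision stays poor either way. At n = 15 an observed r of 0.41 has a 95% CI of about −0.13 to 0.76, and 0.326 gives about −0.22 to 0.72. This limits the benefit but is no reason to discard information from so small an arm.

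The advantage also depends on the model. If response classes were truly distinct and each patient's class known without error, the responder t test would do better (about 0.24 against 0.14 to 0.18 for Spearman). True class is not observed, however; with patients classed by their HAMD-17 change the two approaches are about equal.

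Finally, the SAP lists its groups as pooled, drug only, and drug plus CBT. Its t tests therefore cannot be assumed to describe the 15-patient CBT arm. They are cited here only to show that the SAP adds no continuous analysis.

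**Conclusion.** The point holds as an omission, not as an error in the responder analysis. No planned analysis relates QEEG change to continuous HAMD-17 change, although the score is collected blind and the stated purpose is to measure effect sizes.

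Under bivariate normality the cut costs at least 36% of the information, and about 51% at a 20% response rate. At the effect implied by the plan's own power figures, power is about 0.31 against 0.19 for the rank-based tests. These sizes rest on an assumed response rate, an assumed two-sided alpha of 0.05, a back-solved d of about 0.69 and a linear normal relation. If QEEG change separates only distinct response classes, the gain largely disappears.

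A reader might take one third as a figure fixed by the documents, or conclude that the continuous analysis would rescue the study's power. The documents support neither: they give no response rate from which the loss could be fixed, and an arm of at most 15 remains underpowered, as the protocol concedes.

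**What to change.** Keep the responder analyses as the clinical definition. Add to the plan, as a supportive effect-size estimate and not a further confirmatory test, the Spearman correlation with 95% CI between QEEG change from baseline to week 2 and percent change in HAMD-17 from baseline to endpoint. Give it within each arm, for each metric named in Hypothesis 1.

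The cost is analysis time only, since the data are already part of the collection schedule. The downside is number: three metrics by two arms make at least six estimates, and more if a metric has several versions. Report all of them as estimates with intervals, without selecting on significance. The SAP is dated 2017 and written in the past tense, so if outcome data have already been seen the addition must be labelled post hoc.

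Reconcile the two response cut-offs (more than 50%, and 50% or more) at the same time, and state which SAP group contains the CBT patients so that the within-arm estimates are well defined.
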